16.6.2 Secondary Efficacy Endpoint Analysis

Binary data will be carried out using the Cochran-Mantel-Haenszel (CMH) test stratified by the randomization stratification factors (omalizumab experience for the treatment of CSU [exposed vs. naïve] and UAS7 score [16–27 vs. 28–42]). Data on subjects who experience an ICE prior to the end of Week 12 will be set to non-response status.

Change from baseline in continuous secondary outcomes measured at multiple post-baseline time points will be analyzed longitudinally using a mixed model. The model will include fixed effects for baseline value, randomization stratification factor, treatment, week, the treatment by week interaction, baseline value by week interaction, and allow for random subject effects. The model variance-covariance matrix will be unstructured. However, if computation does not converge, the variance-covariance matrix will take the form of Toeplitz, AR(1), and compound symmetry, whichever converges first. The Kenward-Rogers approach for computing denominator degrees of freedom will be used to account appropriately for pooling of within-subject and between-subject variance estimates. The LS means and the 95% CI for the between-group difference will be estimated for each week.

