To assess the impact of the above "non-responder" rule, the missing data strategy will employ mixed model for repeated measures (MMRM) technique. This approach assumes missing observations are missing at random and borrows information from subjects in the same treatment group considering the missingness of data through the correlation of the repeated measurements. The SAS procedure PROC GLIMMIX will be used for this purpose. The model will include treatment, region, omalizumab experience for the treatment of CSU (exposed, naïve), UAS7 score (16–27, 28–42), visit, and treatment-by-visit-interaction as fixed categorical effects, and baseline and baseline-by-visit-interaction as fixed categorical effects, standard error, two-sided 95% confidence interval for odds ratio and p-values at time points of interest.

All secondary and exploratory efficacy endpoints of continuous nature will utilize MMRM procedure after applying the primary censoring rule, i.e., the rule will censor data after permanent study drug discontinuation or after rescue therapy that applies the censoring rule as described in Section 4.2.5. This censoring rule is equivalent to using all the data up to discontinuation or rescue.

The MMRM model will include fixed effects for baseline value, omalizumab experience for the treatment of CSU (exposed, naïve), UAS7 score (16–27, 28–42), country, treatment, study week, the treatment-by-week interaction, and the baseline-by-week interaction and allow for random subject effects. Treatment and week will each be fitted as categorical variables. The model will assume unstructured covariance structure. If the model with unstructured covariance does not converge, then other covariance structures will be considered to model the within-subject errors. The Kenward-Allakos Inc. Page 36 of 49 *Confidential*

Rogers approach for computing denominator degrees of freedom will be used to account appropriately for pooling of within-subject and between-subject variance estimates. The LS and 95% CI for the difference between groups will be estimated using the simple contrast at each time point. Below is an example of the SAS code for the MMRM:

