proc mixed data=CONTINUOS method=reml; class TREATMENT USUBJID AVISITN REGION USA7_SCORE (16–27, 28–42) OMALIZUMAB_EXPERIENCE; model CHANGE= BASELINE_OF_OUTCOME USA7_SCORE (16–27, 28–42) OMALIZUMAB_EXPERIENCE TREATMENT AVISITN REGION TREATMENT*AVISITN BASELINE_OF_OUTCOME *AVISITN / DDFM=KR; REPEATED AVISITN / SUBJECT=USUBJID (TREATMENT) TYPE=UN; RANDOM REGION; LSMEANS TREATMENT*AVISITN / PDIFF CL; RUN;

Where TREATMENT = planned treatment group in numeric (1 = placebo SC, 2 = lirentelimab SC); AVISITN = time point in Weeks.

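### SAP 6.9.2 drops the protocol's ordered covariance fallback for the HSS7 and ISS7 tests, and its example MMRM code fits region as both a fixed and a random effect

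*SAP*

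**What the plan says.** **Model.** SAP 6.9.2 applies an MMRM to the continuous secondary and exploratory endpoints. Its prose lists the baseline value, the two stratification factors, and then "country, treatment, study week, the treatment-by-week interaction, and the baseline-by-week interaction and allow for random subject effects". It gives no random effect for region. The MMRM in Protocol 16.6.2 has neither region nor country.

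**Code.** The example opens with "proc mixed data=CONTINUOS method=reml". The MODEL statement ends with "OMALIZUMAB_EXPERIENCE TREATMENT AVISITN REGION TREATMENT*AVISITN BASELINE_OF_OUTCOME *AVISITN / DDFM=KR", so REGION is a fixed effect. The next two statements are "REPEATED AVISITN / SUBJECT=USUBJID (TREATMENT) TYPE=UN" and "RANDOM REGION". REGION is the only random effect.

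**Fallback.** For a failed unstructured fit, Protocol 16.6.2 (and the synopsis) provides that "the variance-covariance matrix will take the form of Toeplitz, AR(1), and compound symmetry, whichever converges first". SAP 6.9.2 says instead: "If the model with unstructured covariance does not converge, then other covariance structures will be considered to model the within-subject errors". SAP Section 1 states that the SAP replaces the protocol's statistical methods, standard PK analyses apart.

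**Where it is used.** SAP 5.9 tests the secondary endpoints in the order of SAP 2.2, each at two-sided 0.05, once the primary is significant. HSS7 and ISS7 come first and second and use this MMRM. The third, UAS7 = 0, uses a CMH test. Under SAP 5.6 the sponsor's analysts receive the randomization code after database lock, and analysis starts then.

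**The concern.** Two things look wrong, and they are separate.

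First, the fallback. Choosing among covariance structures changes the SE, the degrees of freedom and the p-value of the Week 12 contrast. The protocol closed that choice; the SAP, which governs, reopens it. Convergence on the real data becomes known only once analysis starts, when the randomization code is available. HSS7 and ISS7 head the testing sequence, so the choice also bears on whether UAS7 = 0 is formally tested at all.

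Second, the code. A factor that is already a fixed effect leaves no information for a random effect of the same factor. The fitted model would carry a variance component that the data cannot estimate, and the prose does not ask for it.

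**Working it through.** **1. The plan's own figure.** The documents give no figure for this model. The one design figure is power above 90% for the primary endpoint (SAP 3.4: 55 per group, difference 8, SD 11). It reproduces: 8 / (11 × √(2/55)) = 3.81; 3.81 − 1.96 = 1.85; power 0.968 (0.966 by noncentral t with 108 df). Nothing below depends on it.

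**2. Why the region variance is not identifiable.** Let X be the fixed-effect matrix and Z the region indicators. REML uses only contrasts K′y with K′X = 0. With REGION in MODEL, Z = XB for some matrix B, so K′Z = 0, and the region variance σ² drops out of the likelihood.

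Count the columns for 12 weeks and two regions (U.S., non-U.S., SAP 5.10): 12 week + 12 treatment-by-week + 12 baseline-by-week + 1 omalizumab + 1 UAS7 stratum + 1 region = 39. Adding Z leaves the rank at 39. With three countries, both ranks are 40.

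**3. What that does to the estimates.** With V = R + σ²ZZ′ and Z = XB, the covariance of the fixed-effect estimates is (X′R⁻¹X)⁻¹ + σ²BB′.
- Treatment contrast: the rows of B for treatment are zero, so the difference and its SE do not depend on σ².
- Arm LS mean, averaged equally over regions: the added variance is σ² × (1/4 + 1/4) = σ²/2 with two regions, and σ² × 3 × (1/9) = σ²/3 with three countries.

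**4. Numerical check.** The data were simulated, with assumed values throughout: 130 subjects, 12 weeks, SD 5.5, a fixed within-subject covariance, and 79% of subjects in the U.S. Two regions, REGION fixed and random:

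| σ² | REML log-likelihood | Week 12 difference (SE) | Arm LS-mean SE |
|---|---|---|---|
| 0 | −2587.839 | −3.002 (0.979) | 0.85 |
| 1 | −2587.839 | −3.002 (0.979) | 1.10 |
| 10 | −2587.839 | −3.002 (0.979) | 2.39 |
| 100 | −2587.839 | −3.002 (0.979) | 7.12 |

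The last column follows step 3: √(0.8462² + 1/2) = 1.10. The likelihood is still the same at σ² = 10000. With REGION random only, it does move, from −2588.49 at σ² = 0 to −2592.79 at σ² = 10000, so the flatness comes from the double entry. With three countries it is again flat, at −2549.804.

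**5. The fallback.** SAP 5.2 defines diary windows for Weeks 1 to 12, and the code measures time in weeks. If all 12 are modelled:
- unstructured: 12 × 13 / 2 = 78 parameters
- Toeplitz: 12
- AR(1): 2
- compound symmetry: 2

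If only the seven post-baseline visits through Week 12 are modelled, the unstructured count is 7 × 8 / 2 = 28. The SAP does not settle which applies.

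**The case against.** **The code is only an example.** SAP 6.9.2 says so. It also cannot run as printed, because the UAS7 stratum is written with its score ranges in brackets after the variable name. A programmer has to rewrite it, and the prose has no random region. This is fair and limits the weight of the coding point. But it is the only coded form of this model, and the independent reprogramming in SAP Section 7 would not expose the error if both programmers start from the same code.

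**The tests are not touched.** Given the within-subject covariance, the treatment difference and its SE are the same at every region variance. This stands in full. A reader might infer from the double entry that the HSS7 and ISS7 tests are biased or mis-sized; the algebra does not support that.

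**A flat direction need not stop the fit.** A reader might also infer that the redundant term makes the model fail and so triggers the fallback. That is unproven. Software may set the variance to zero with a warning and converge on everything else, and a Hessian warning is not the non-convergence that the SAP names as the trigger. Kenward-Roger uses the information matrix of the covariance parameters, which is singular here unless that variance is fixed. The behaviour was not tested in SAS.

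**Departures must be reported.** SAP Section 1 and SAP 5.1 require changes from planned methods to be documented. That makes a switch visible afterwards; it does not set the order beforehand. The SAP sentence is also broad enough to include the protocol's three structures, but it binds nobody to them or to their sequence.

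**Conclusion.** The point holds in a limited form and is minor.

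The more important part is the fallback, and it rests on the SAP text itself. The governing document gives no list and no order, where the protocol gave both. If the unstructured model fails, the covariance for two fixed-sequence tests is chosen after unblinding. How far a p-value could move cannot be stated from the documents, which give no covariance for HSS7 or ISS7. The count of 78 parameters for about 130 subjects shows why a fallback is needed. It does not show that failure is likely, and it has nothing to do with the redundant term.

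The coding part is certain as algebra and small in effect. The region variance is not identifiable whatever the region split or covariance. The exposure is in the arm LS-mean SEs and their intervals: σ²/2 added to the variance with two regions, σ²/3 with three countries, nothing if the software returns zero. The simulated SEs illustrate this and are not forecasts. Sample size and power do not change.

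**What to change.** Amend SAP 6.9.2 before the database lock that releases the randomization code:

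1. Delete "RANDOM REGION" and keep the REPEATED statement with TYPE=UN, which already carries the within-subject correlation.
2. Use either region or country as the fixed effect, the same in prose and code. The prose now says country and the code REGION.
3. Replace the open fallback sentence with the protocol's sequence after unstructured: Toeplitz, then AR(1), then compound symmetry, stopping at the first that converges.

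The cost is one code line, one term made consistent and one sentence. Region stays adjusted for as a fixed effect if that option is chosen, and removing the random term leaves the tested difference as it was (−3.002, SE 0.979 in the check above). SAP 5.1 already allows for an amendment of this kind before lock.

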6.10 Analysis of Pharmacokinetic Endpoint

The analysis of the PK concentration will be based on the Safety population. Lirentelimab SC concentrations will be listed by treatment, subject, nominal time, and actual time. Concentrations that are below limit of quantification (BLOQ) will be indicated in the listing.

Plasma concentrations will be summarized at each nominal time point separately for each treatment. The following descriptive statistics will be presented: n, arithmetic mean, SD, geometric mean, % CV, median, minimum, and maximum.

Individual plasma concentration vs. actual times will be plotted for each subject in linear and semilogarithmic scales, placed on the same page. Mean plasma concentration at the scheduled time points will be plotted for each treatment in linear and semi-logarithmic scale, with the associated standard errors (for linear scale only) at each scheduled time point.

In the plot, concentrations that are BLOQ will be assigned a value of 0 if they are collected predose or assigned a value of 1/2 the lower limit of quantification (LLOQ) if they are collected postdose.

Analysis of PK parameters are specified separately in a PK analysis plan.

6.11 Safety Analyses

6.11.1 Adverse Events

Safety assessments will be based mainly on the nature, frequency, relationship, and severity of adverse events (AE). The AE will be coded by primary System Organ Class (SOC) and Preferred Term (PT) according to MedDRA (version 21.0). The treatment-emergent adverse events (TEAE) will be summarized by the number and percentage (n and %) of subjects in each SOC and PT.

For summaries by relationship to study drug, "possibly related" will be combined with "related", and "unlikely/remotely related" will be combined with "not related." When multiple AE are reported with the same PT, the AE of the strongest relation to study drug will be included in the summary by relationship, and the AE of the most severe grade will be included in the summary by severity table.

The following AE incidence tables will be presented.

- Overview of TEAE to include
 - Number (%) of subjects who reported at least 1 TEAE
 - Number (%) of subjects who reported at least 1 treatment related TEAE
 - Number (%) of subjects who reported at least 1 severe TEAE
 - Number (%) of subjects who reported at least 1 serious TEAE
 - Number (%) of subjects who reported at least 1 TEAE leading to treatment discontinuation
 - Number (%) of subjects who reported at least 1 TEAE leading to study discontinuation
 - Number (%) of subjects who reported at least 1 TEAE of special interest (TEAESI)
- TEAE by PT sorted by decreasing order of subject incidence in the combined treatment group
- TEAE by SOC and PT in alphabetical order
- TEAE by SOC, PT, and maximum severity
- TEAE by SOC, PT, and strongest relationship to study drug
- TEAE leading to treatment discontinuation by SOC and PT, if warranted by sample size
- TEAE leading to study discontinuation by SOC and PT, if warranted by sample size
- Serious TEAE by SOC and PT, if warranted by sample size
- TEAESI by SOC and PT

All AE will be listed with onset/stop day, relationship to study drug, severity, action taken, and outcome. Pertinent subject information including treatment group and demographics will also be included.

Separate listings will be provided for TEAE leading to study discontinuation, TEAE of special interest, and treatment-emergent serious AE (TESAE).

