4.4 Safety Objectives

To evaluate the safety and tolerability of lirentelimab in adult subjects with H1-AH refractory CSU by determining AE incidence and severity, study withdrawals due to AE, changes in vital signs and laboratory tests including immunogenicity, changes in concomitant medication beginning on or after the first injection of study drug, and other safety parameters.

Safety and tolerability will be assessed throughout the study by monitoring and evaluating AE, including any reactions to the SC injection. All TEAE will be collected from the start of study drug administration through Day 155 (\pm 5 days) or Early Termination (ET) during the double-blind period of the study.

Severity will be assessed using the National Cancer Institute (NCI) Common Terminology Criteria for Adverse Events (CTCAE) tables and toxicity grading scale (version 5 or the current version). All AE will be assigned a severity grade and will be assessed to determine whether they are clinically significant and related to study drug.

Additional safety evaluations include clinical laboratory tests comprising anti-drug antibody (ADA) to lirentelimab SC, complete blood counts, chemistries, and urinalyses; physical exams; and vital sign measurements.

The Medical Monitor will review blinded safety data throughout the study. Certain safety data (post-treatment cell differentials) collected during the double-blind period of the study will not be provided to study sites or to the Sponsor as it may cause bias. The designated Safety Monitor

will review blinded safety data as well as post-treatment cell counts and will escalate to the Medical Monitor, as needed, in a manner that does not cause bias.

An independent Data Monitoring Committee (iDMC) has been convened and will meet in accordance with the iDMC charter.

5. Study Design

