14.1 Adverse Events

In accordance with 21 Code of Federal Regulation (CFR) 312.32(b) and International Conference on Harmonization (ICH) Guidance E2A, an AE is any untoward medical occurrence in a clinical investigation of a subject administered a pharmaceutical product and that does not necessarily have a causal relationship with the treatment.

An AE is therefore any unfavorable and unintended sign (including an abnormal laboratory finding), symptom, or disease temporally associated with the administration of an investigational product, whether or not related to that investigational product. An unexpected AE is one of a type not identified in nature, severity, or frequency in the current Investigator's Brochure or of greater severity or frequency than expected based on the information in the Investigator's Brochure.

Examples of an AE include:

- Significant worsening or exacerbation of underlying medical condition.
- Significant abnormal findings from physical exams, vital signs, or laboratory tests.

The following examples are not considered AE:

- Medical or surgical procedure, although the condition leading to the procedure is usually an AE.
- Anticipated day-to-day fluctuations of preexisting medical conditions (including laboratory values) as long as significant worsening from baseline does not occur.
- Signs or symptoms of the disorder being studied unless they become more severe or occur with greater frequency than occurring at baseline.

All AE, whether elicited by questions from study staff, volunteered, or noted on physical examination/laboratory testing, and regardless of causality or severity, will be assessed and recorded in the eCRF beginning after the first administration of study drug in the double-blind period of the study and ending at the time of study completion or ET of the double-blind period or the OLE period, whichever is later.

For subjects participating in the OLE period, AE will be recorded in the CRF of the AK002-027 double-blind treatment period database up until the first administration of lirentelimab in the OLE period and recorded in the CRF of the AK002-027 OLE period database beginning from the time of first administration of lirentelimab ending at the time of study completion or ET of the OLE period.

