14.8 Adverse Event Reporting Procedures

14.8.1 All Adverse Events

Any clinically significant AE that is ongoing at the time of study completion or ET will be followed by the Investigator until event resolution, the AE is otherwise explained, not considered clinically significant by the Investigator, or the subject is lost to follow-up.

All AE identified, whether serious or non-serious, will be recorded in the AE eCRF beginning from the first administration of study drug in the double-blind period of the study and ending at the time of study completion or ET of the double-blind period or the OLE period, whichever is

later. Serious adverse events considered related to screening procedures will be recorded in the AE eCRF starting on the date of informed consent. Whenever appropriate, the CTCAE (version 5.0 or most current version) should be utilized for naming common AE (Appendix 6).

For subjects participating in the OLE period, AE will be recorded in the CRF of the AK002-027 double-blind treatment period database until the first administration of lirentelimab in the OLE period and recorded in the CRF of the AK002-027 OLE period database beginning at the time of the first administration of lirentelimab.

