16.7 Safety Analysis

Subject incidence of TEAE will be tabulated by the Medical Dictionary for Regulatory Activities (MedDRA) system organ class (SOC) and preferred term, and by severity and treatment relationship. Serious TEAE and TEAE leading to study discontinuation will be listed with pertinent information. Change from baseline in laboratory tests will be summarized with descriptive statistics. Details will be provided in the SAP.

Adverse Events: All AE will be coded using MedDRA and will be classified by MedDRA SOC and preferred term. Listings will include all AE collected on study. The summaries of AE will be based on TEAE, defined as an AE reported in the clinical database with a date of onset (or worsening) on or after the start date of the first SC injection of study drug.

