20.9.5 OLE Exclusion Criteria

Subjects are not permitted to participate in the OLE period if any of the following criteria are met:

- 1) Previous administration of the study drug (lirentelimab or placebo) was poorly tolerated by the subject, in the opinion of the Investigator.
- 2) Any other reason that in the opinion of the Investigator or Medical Monitor makes the subject unsuitable for participation in the OLE period.

Acceptable documentation required to confirm inclusion and exclusion criteria will be further explained in the Study Reference Manual.

20.9.6 **OLE Treatment**

Formulation, storage, preparation, and administration of the open-label lirentelimab SC for the OLE will be consistent with Section 10 of the protocol and the AK002-027 Pharmacy Manual.

The first OLE study drug administration of open-label 300 mg lirentelimab SC will be done on Day 85 of the double-blind period. This will be considered Day 1 of the OLE period. OLE dosing may be delayed for up to 7 days after the completion of the Day 85 visit. The subsequent injections will occur on OLE Days 15, 29, 43, 57, and 71 (±5 days).

The subject will be observed for at least 1 hour (or longer as per Investigator's discretion) after the end of the injection. In the event of an IRR, the subject may require prolonged observation (>1 hour or until symptoms resolve), as per Investigator's discretion. Subjects will also be instructed to immediately contact the study doctor if any reactions occur after discharge.

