2.2 Secondary Objectives and Endpoints

[figure not shown]
The secondary objectives of the study are to further characterize the efficacy and safety of lirentelimab SC in adult subjects with CSU as measured by the following:

- Improvement of severity of hives assessed as absolute change from baseline in HSS7 at Week 12
- Improvement of severity of itch assessed as absolute change from baseline in Itch Severity Scale (ISS7) at Week 12
- Absence of hives and itch at Week 12 assessed as proportion of subjects achieving UAS7 = 0
- Occurrence of treatment-emergent adverse events (TEAE) and serious adverse events (SAE), laboratory values, vital signs, and physical examinations during the study

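### SAP 6.11.1 gives TEAEs by arm as crude percentages with no end of window, while double-blind AE follow-up differs by OLE entry, a choice made after randomization

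*SAP*

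**What the plan says.** - **Summary measure.** SAP 6.11.1 states that TEAEs "will be summarized by the number and percentage (n and %) of subjects in each SOC and PT", and its overview rows have the same form ("Number (%) of subjects who reported at least 1 TEAE"). Neither the text nor the table list in SAP Appendix 2 has a person-time rate, a time-to-event summary or a Day 85 cut-off for adverse events.
- **TEAE definition.** Protocol 16.7 counts events "with a date of onset (or worsening) on or after the start date of the first SC injection of study drug". That fixes the start of the window but not its end.
- **Follow-up without the OLE.** Protocol 4.4: "All TEAE will be collected from the start of study drug administration through Day 155", or to early termination. Protocol 13.13 and 14.2 tie follow-up after an early stop to 84 days after the last dose.
- **Follow-up with the OLE.** Protocol 14.1 records AEs in the "double-blind treatment period database up until the first administration of lirentelimab in the OLE" period, and Protocol 14.8.1 says the same. OLE dosing may start at the Day 85 visit or up to 7 days later (Protocol 13.11). Entrants then count as double-blind completers (Protocol 15.1).
- **Who enters.** Entry is optional and needs continued eligibility (Protocol 20.9.4). It is barred if "Previous administration of the study drug (lirentelimab or placebo) was poorly tolerated by the subject", in the investigator's opinion (Protocol 20.9.5).
- **Status.** SAP 2.2 lists as a secondary endpoint "Occurrence of treatment-emergent adverse events (TEAE) and serious adverse events (SAE), laboratory values, vital signs, and physical examinations during the study".
- **Locks.** Protocol 17.4 plans a provisional lock for safety and efficacy through Day 85 and a final lock for safety data after Day 85. SAP 5.6 describes one lock, after the whole double-blind period.

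**The concern.** The percentage of subjects with an event rises with time observed. Here that time depends on a decision each subject makes after about 12 weeks on the assigned treatment. If symptom relief or tolerability makes one arm more likely to enter the OLE, that arm is observed for less time and shows a lower TEAE percentage, even when the drug has no effect on adverse events. The comparison would then mix drug effect with follow-up in a listed secondary endpoint, and the error could go in either direction.

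The missing window end is a second problem. The two separate databases imply a cut at the first OLE dose, but no TEAE text states it. Read literally, the definition would let events on open-label lirentelimab count under the placebo arm.

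**Working it through.** The plan gives no figure for AE incidence or OLE uptake, so there is none to reproduce beyond the visit days. Incidence, uptake and hazard shape below are assumptions.

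**1. Follow-up times (Protocol Table 1).** Last dose is Day 71.
- OLE entrants: 71 + 14 = Day 85. With the ±5-day visit window and the 7-day allowance, the range is Day 80 to 97.
- Non-entrants who complete dosing: 71 + 84 = Day 155. The ratio is 155/85 = 1.82, or 155/92 = 1.68 if the OLE starts 7 days late.
- Early stoppers: after Dose 1, 1 + 84 = Day 85; after Dose 2, 15 + 84 = Day 99.

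**2. Model with no drug effect.** Let I(t) be the probability of at least one TEAE by day t, the same in both arms, and u the proportion entering the OLE, unrelated to earlier AEs. Then

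crude % = u × I(85) + (1 − u) × I(155)

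spurious gap = (u_high − u_low) × [I(155) − I(85)]

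The arm with lower uptake shows the higher percentage.

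**3. Worked example, constant hazard, I(155) = 50%.** λ = −ln(0.5)/155, so I(85) = 1 − exp(−85λ) = 31.6%.
- Uptake 80% in both arms: 35.3% vs 35.3%, gap 0.
- 80% vs 60%: mean follow-up 99 vs 113 days; 35.3% vs 39.0%, gap 3.7 points.
- 90% vs 50%: mean follow-up 92 vs 120 days; 33.5% vs 40.8%, gap 7.4 points before rounding.

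**4. Range.** In the last two rows the hazard after Day 85 is 0.3 times the earlier one, so I(155) = 1 − [1 − I(85)] × exp(−0.3 × 70λ), with λ = −ln[1 − I(85)]/85.

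| Hazard | I(85) | I(155) | Gap, 80% vs 60% | Gap, 90% vs 50% |
|---|---|---|---|---|
| Constant | 17.8% | 30% | 2.4 | 4.9 |
| Constant | 31.6% | 50% | 3.7 | 7.4 |
| Constant | 48.3% | 70% | 4.3 | 8.7 |
| Falls to 0.3 | 30% | 35.9% | 1.2 | 2.4 |
| Falls to 0.3 | 50% | 57.9% | 1.6 | 3.1 |

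A falling hazard is plausible. Non-entrants get no injections after Day 85, and injection-related and injection-site reactions are defined within 24 hours of an injection (Protocol 14.4, 14.5). Scheduled visits drop from seven post-baseline visits through Day 85 to two afterwards.

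**5. Would pooled exposure-adjusted rates solve it?** Take the last row with 90% vs 50% uptake. Expected events per subject, divided by mean follow-up and expressed relative to the on-treatment rate:
- 90% uptake: (85 + 0.1 × 70 × 0.3)/92 = 87.1/92 = 0.947
- 50% uptake: (85 + 0.5 × 70 × 0.3)/120 = 95.5/120 = 0.796

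The rate ratio is 0.796/0.947 = 0.84 with no drug effect. The crude percentages are 53.9% vs 50.8%, ratio 1.06. Pooled rates are therefore further off here, and in the opposite direction.

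**6. Common window.** If every subject is counted only to Day 85 or the first OLE dose, both arms show I(85) and the gap from this route is zero for any uptake.

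**The case against.** The best counter-arguments, and what stands of each:

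- **Safety is descriptive.** Protocol 16 excludes formal inference on safety, and SAP 6.11.1 plans no between-arm test. That stands: no error rate is at risk. The side-by-side percentages will still be read as a comparison. SAP 5.9 sends the Section 2.2 endpoints through ordered testing without excluding the safety item, but it names no test for it, so this point does not rest on that.
- **The protocol already has a Day 85 cut.** Protocol 17.4 does separate safety through Day 85 from later safety. The SAP has one lock, says it supersedes the protocol's statistical methods (SAP 1), and uses no Day 85 cut in any AE table. Whether lock timing is a statistical method is arguable, so the passages need reconciling.
- **The effect is conditional and may be small.** This stands. The documents give no reason to expect 90% vs 50% uptake. With 65 per arm and 50% incidence, the standard error of a difference is √(2 × 0.25/65) = 8.8 points, so the bias may lie within sampling noise.
- **The data can be re-cut.** AE listings carry onset day and treatment group, so a Day 85 window can be rebuilt. That is true, but it should be specified before unblinding.

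A reader might also infer that the tolerability bar gives subjects with AEs the longer follow-up and so inflates the any-TEAE row. The documents do not support that. A subject with a TEAE before Day 85 is already counted, so selecting such subjects out of the OLE shrinks the gap. If every non-entrant already had one, the gap is zero. Those who stop dosing early are also followed only to 84 days after the last dose, which can be close to an OLE entrant's follow-up. Selection on tolerability can matter for individual SOC and PT rows, where a subject can still add a new event.

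**Conclusion.** The concern holds. Following SAP 6.11.1 as written puts unequal follow-up, set by a post-randomization choice, into the between-arm TEAE percentages, and the end of the TEAE window is undefined. With no drug effect, the spurious difference is about 1 to 9 points (1.2 to 8.7 in the table). That range assumes uptake of 80% vs 60% to 90% vs 50%, uptake unrelated to earlier AEs, and the incidences and hazard shapes shown. It is zero when uptake and hazards are equal in the two arms.

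Two stronger readings should be resisted. The upper end is not an expected bias: it needs a constant hazard, high incidence and very unequal uptake, and a falling hazard brings the range to about 1 to 3 points. Nor are the safety results unusable, since the onset days are recorded. This is worth correcting before unblinding and does not touch the primary efficacy analysis.

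**What to change.** In SAP 6.11.1:

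1. State the end of the TEAE window, and say explicitly that events from the first OLE dose onward are not double-blind TEAEs.
2. Make the main between-arm TEAE tables cover first dose to the earlier of the Day 85 visit and the first OLE dose, for all subjects. State which date stands in when there is no Day 85 visit.
3. Tabulate double-blind events after Day 85 separately, for subjects who do not enter the OLE, with their number as denominator.
4. If exposure-adjusted rates are added, restrict them to the common window or report them by period. Do not pool them over the unequal follow-up.
5. Reconcile SAP 5.6 with Protocol 17.4 on whether there is a Day 85 lock.

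The cost is SAP wording and a few extra tables, with no new data. The small downside is that late follow-up events leave the main table for their own. Dropout before Day 85 (the plan expects up to about 10% dropout) still leaves some unequal follow-up inside the common window.
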